- ^b All subjects should be followed up following delivery or at termination of pregnancy for EIU assessment. In case of no associated serious adverse events (SAE), the follow-up visit should take place within 14 calendar days after expected date of delivery or termination of pregnancy.
- ^c Ultrasound will be performed only if the urine pregnancy test is positive.
- ^d Peripheral blood smears (thick and thin) will be prepared at visits on Day 0 (predose) and weekly intervals afterwards. Two smears per subject at each time point.
- ^e If not done at any prior ANC visit for this pregnancy.
- ^f The blood blot will be collected at baseline (predose) and each visit through Day 42 but evaluated only if positive by the blood smear following initial clearance.
- ^g The first dose on Day 0 and the third dose on Day2 will be administered under supervision by investigator at the antenatal care (ANC) clinic, and the second dose on Day 1 will be administered at home under supervision of a field worker(s).
- ^h PK evaluation will be conducted on blood samples collected from the subjects who consented for such test. Insert intravenous catheter as deemed necessary. Subjects who received even one dose will be followed up for all subsequent PK sample collection. The exact date and time of blood sample collection will be recorded.
- ⁱ Two PK blood specimens (one for AZ and one for CQ and desethyl-CQ analyses) will be collected at predose.
- ^j Two PK blood specimens (one for AZ and one for CQ and desethyl-CQ analyses) will be collected at predose, 2 hours (as close to 2 hours as possible) and 8 hours (window: 4 to 12 hours) following dosing on Day 2.
- ^k Two PK blood specimens (one for AZ and one for CQ and desethyl-CQ analyses) will be collected at visits on Days 7 and 14 (a random time point), and only blood sample (for CQ and desethyl-CQ analyse) will be collected on Days 21 and 28 samples (a random time point).
- ^l EIU assessment: Every attempt should be made to follow up the subject following delivery or pregnancy termination. In case of no associated serious adverse events (SAE), subjects should be followed up by fieldworkers at clinic or at home within 14 calendar days after expected date of delivery or termination of pregnancy. EIU assessment includes maternal information, delivery and neonatal information. Fetal information will be collected in the event of pregnancy termination.

TABLE OF CONTENTS

1. INTRODUCTION	13
1.1. Indication	13
1.2. Background.....	13

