1.2. Background

Malaria is a serious protozoal infection caused by any of the five species of *Plasmodium* and transmitted by anopheline mosquitoes. *Plasmodium falciparum* is one of the leading causes of deaths world-wide caused by a single causative agent.^{1,2} As per the World Health Organization (WHO) *World Malaria Report 2009*,³ about half of the world's population is at risk of infection in 108 endemic countries and territories. There were an estimated 243 million cases and 863,000 malaria-related deaths in 2008.³ Africa has the largest number of people living in high-risk areas and the most the malaria deaths. Pregnant women are more prone to malaria than non-pregnant women, especially during their first and second pregnancies. Malaria in pregnancy (MIP) is one of the most common causes of preventable morbidity and mortality in pregnant women and infants in sub-Saharan Africa. An estimated 30 million pregnancies are at risk of malaria infection in the region each year;⁴ about 200,000 infants and 10,000 women die of malaria in pregnancy each year.⁵

Intermittent Preventive Treatment in Pregnancy (IPTp) is one of the four key strategies recommended by the WHO's Global Malaria Program for malaria control in high transmission areas, where approximately 1 in 4 pregnant women are parasitemic at any given time, but remain mostly asymptomatic.⁶ Placental infection is of particular concern to fetal development and can only be diagnosed post-partum by placental histological examination. IPTp is based on administration of a complete curative dosing regimen of an antimalarial medicine at periodic intervals during pregnancy regardless of whether or not pregnant women are infected with malaria. IPTp has two primary objectives: (1) to clear asymptomatic peripheral and placental parasitemia, and (2) to provide intermittent chemoprophylaxis against malaria infection during pregnancy.⁴

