6.1.3. Days 2 Visit (at ANC clinic/center)

- Assess adverse events;
- Concomitant treatment history;
- Oral temperature;
- If a subject presents with symptoms of malaria (fever $>37.5^{\circ}\text{C}$, oral), no further AZCQ dose would be given. The subject would be immediately referred to the investigator for parasite counts and appropriate treatment for malaria in pregnancy as per national/ local guidelines;
- Administer treatment: third dose of AZCQ;
- Two blood samples (one for AZ and one for CQ and desethyl-CQ analyses) from the subjects who consented for PK analysis at each of the following timepoints: predose, 2 hours (as close to 2 hours as possible) and 8 hours (window: 4 to 12 hours). The exact date and time of blood sample collection will be recorded.

6.1.4. Follow-up Visits on Days 7, 14, 21, 28, 35, 42 at ANC clinic/center)

- Assess adverse events;
- Concomitant treatment history;
- Limited physical examination (only on Days 42);
- Oral temperature;
- Hemoglobin (with HemoCueTM) (only on Day 42);
- Thick and thin peripheral blood smears for parasite identification and counts (2 smears at each visit);
- If a subject presents with symptoms of malaria (fever $>37.5^{\circ}\text{C}$, oral), and has parasitemia (microscopy), she will receive standard antimalarial treatment according to the local treatment guidelines for malaria in pregnancy;
- A dried blood blot will be collected at each visit for potential molecular testings;

- Two blood samples (one for AZ and one for CQ and desethyl-CQ analyses) on Days 7 and 14 (a random time point) from the subjects who consented for PK analysis. The exact date and time of blood sample collection will be recorded;
- One blood sample (for CQ and desethyl-CQ analyses only) on Days 21 and 28 (a random time point) from subjects who consented for PK analysis. The exact date and time of blood sample collection will be recorded.

6.1.5. Unscheduled Visits through Day 42

Any subject who develops signs and symptoms of malaria (fever ($>37.5^{\circ}\text{C}$, oral) and new signs and symptoms of malaria including malaise, headache or abdominal pain at any time other than the scheduled visits through Day 42, will be required to report to the investigator/study staff immediately for further evaluation. Blood smears and blood blots will be collected. The subject will be treated with the current standard of care for malaria in pregnancy.

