7.1. Parasite Clearance Assessments

The primary tool for assessing the parasitological clearance is the peripheral blood smear (thick and thin), which will be prepared at the study sites with the standard Giemsa staining for parasite identification and count using white blood cell counting method on thick smears. Each blood smear will be read by two microscopists in a blinded fashion (blinded to the reading of other microscopists). In the event of discrepancy, the slide will be read by third microscopist and parasite density will be calculated by averaging the two most concordant counts. All the smears will be preserved for possible third party confirmation. Refer to the Laboratory Manual for details. If and when the blood smears become positive after initial parasite clearance, the blood blot collected at that visit will be tested for molecular genotyping assays to differentiate the recrudescence from reinfection.

- Recrudescence: Reappearance of asexual *P. falciparum* blood stage parasites confirmed by the results of molecular testing. This finding reflects that the subject failed the treatment since the original parasite recurred;
- Reinfection: Infection by a different genotypic parasite as documented by molecular testing. This finding reflects that the subject did not fail treatment since a molecularly distinct parasite was found at the time of recurrence.

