9.2.1. Analysis of Primary Endpoint

The proportion of subjects with parasitological response (PCR corrected) at Day 28 post first dose of study medication will be estimated for the primary endpoint using the MITT and PP subject populations. The proportion will be estimated from the Kaplan-Meier curve based on the time to the first occurrence of parasitological failure (PCR corrected). Use of the Kaplan-Meier curve/product limit estimator is recommended by WHO⁸ and has been used in analyzing primary efficacy endpoints in late stage antimalarial treatment clinical trials.⁹²⁻⁹⁴

A subject will be a parasitological responder if she has a zero parasite count on the Day 7 visit without subsequent recrudescence (PCR corrected) through the day of consideration, otherwise she is a parasitological failure. In addition, subjects who withdraw from the study treatment during the first three days due to development of malaria symptoms and are administered antimalarial standard of care treatment for malaria in pregnancy, will be considered parasitological failures. The time (number of days) to the first occurrence of parasitological failure will be the analysis variable. The time in days is defined as [date of the parasitological failure event – date of the first dose of study medication + 1].

Subjects who do not experience the defined event (parasitological failure) will be censored as follows:

- Subjects who withdraw from the study early due to any reason will be censored on the day of the last available blood smear measurement;
- Subjects who continue on in the study but have all remaining blood smears missing from a given point in time onward will be censored on the day of the last available smear;
- Subjects completing the Day 42 visit post first dose of study medication will be censored on the day of the last available blood smear measurement;
- Subjects receiving any concomitant antimalarial for reinfection (PCR corrected) or in the absence of parasitemia will be censored at the visit date if the antimalarial is given after collection of the blood smear on that day. Otherwise the subject will be censored on the day of the last available previous blood smear measurement;
- Subjects who are lost to follow-up without any follow-up blood smears will have a censored duration of 1 day.

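### Reinfection is censored only when an antimalarial is given, so the same PCR-confirmed event is handled two ways; the PCR-corrected response can be slightly overstated if later recrudescence is hidden

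*Protocol*

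**What the plan says.** Under 9.2.1 the definition of a responder requires: "zero parasite count on the Day 7 visit without subsequent recrudescence (PCR corrected) through the day of consideration, otherwise she is a parasitological failure". Section 7.1 says of reinfection: "This finding reflects that the subject did not fail treatment since a molecularly distinct parasite was found at the time of recurrence". Reinfection is therefore not an event in the PCR-corrected analysis.

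The one censoring bullet that mentions reinfection reads "Subjects receiving any concomitant antimalarial for reinfection (PCR corrected) or in the absence of parasitemia will be censored at the visit date" (with an earlier date if the drug came before that day's smear). No bullet is triggered by reinfection itself. A reinfected woman who takes no antimalarial and finishes follow-up falls under "Subjects completing the Day 42 visit post first dose of study medication will be censored on the day of the last available blood smear measurement". Section 9.2.2 carries the same censoring over to the secondary PCR-corrected analyses.

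On treatment at the Day 7 to Day 42 visits, 6.1.4 says that a woman who presents with symptoms (fever) "and has parasitemia (microscopy), she will receive standard antimalarial treatment according to the local treatment guidelines for malaria in pregnancy". Section 1.2 describes high-transmission areas as places "where approximately 1 in 4 pregnant women are parasitemic at any given time, but remain mostly asymptomatic".

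On genotyping, 7.1 says "If and when the blood smears become positive after initial parasite clearance, the blood blot collected at that visit will be tested". Footnote f of the Schedule of Activities has the blot collected at baseline and "each visit through Day 42 but evaluated only if positive by the blood smear following initial clearance".

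**The concern.** Take two women with the same PCR-confirmed reinfection on Day 14. One has fever and is treated after the smear; she is censored on Day 14. The other has no symptoms and is not treated; she stays in the risk set to Day 42, which is 42 − 14 = 28 further days counted as response while she may be smear-positive. What separates them is symptoms and later treatment, not the event. Section 1.2 says acquired immunity contributes to the efficacy of partially effective drugs, so this split may be related to failure risk.

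Keeping the untreated woman at risk is harmless as long as a later recrudescence in her can still be seen. If the new infection keeps the smear positive and the original strain is not picked up, she adds to the Kaplan-Meier denominator without being able to add to the numerator. The recrudescence hazard is then too low and the PCR-corrected response too high, more so at Days 35 and 42 than at Day 28.

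A lesser point is that a treated reinfected woman who completes Day 42 meets both the antimalarial bullet and the completer bullet, which give different dates, and 9.2.1 states no order of precedence.

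**Working it through.** **Scale.** The protocol gives no figure for this rule, so the planned precision serves as the yardstick. Its sample size reproduces: (1.960 + 0.842)² × 0.95 × 0.05 / 0.05² = 149.1 evaluable, and 149.1 / 0.90 = 165.7, against the stated 166 (9.1). At 95% response and 149 evaluable, the half-width is 1.96 × √(0.95 × 0.05 / 149) = 3.5 points.

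**Model.** There are visits at Days 14, 21, 28, 35 and 42. Let h be the recrudescence risk per visit, q the reinfection risk per visit, u the share of reinfections untreated, N the women not reinfected and U the untreated reinfected women still in the risk set. With full masking the rule as written estimates

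hazard = h × N / (N + U),

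while the true recrudescence-free proportion after k visits is (1 − h)^k. The protocol gives no rates for AZCQ in pregnancy, so h, q, u and the degree of masking are assumptions.

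**One case in full: h = 2%, q = 5%, u = 100%.**
- Day 14: N = 1, U = 0; hazard 0.0200; response 0.9800.
- Day 21: N = 0.98 × 0.95 = 0.9310, U = 0.98 × 0.05 = 0.0490; hazard 0.02 × 0.9310 / 0.9800 = 0.0190; response 0.9614.
- Day 28: N = 0.9310 × 0.98 × 0.95 = 0.8668, U = 0.0490 + 0.9310 × 0.98 × 0.05 = 0.0946; hazard 0.0180; response 0.9440.
- Truth at Day 28: 0.98³ = 0.9412. Difference +0.29 points.
- Two further visits give 91.29% at Day 42 against 0.98⁵ = 90.39%. Difference +0.90 points.

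**Other rates, full masking.**

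| h | q | u | Day 28: written vs true | Day 42: written vs true |
|---|---|---|---|---|
| 1% | 5% | 80% | +0.1 | +0.4 |
| 1% | 10% | 100% | +0.3 | +0.9 |
| 2% | 5% | 80% | 94.35 vs 94.12 (+0.2) | 91.13 vs 90.39 (+0.7) |
| 2% | 10% | 100% | 94.68 vs 94.12 (+0.6) | 92.10 vs 90.39 (+1.7) |

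**Rates closer to figures quoted in the protocol** (cumulative to Day 28, spread over three visits, all reinfections untreated, full masking):
- 2% recrudescence and 3% reinfection, the latter being the corrected-to-uncorrected gap of 98% to 95% in study A0661134 (1.5.2.2): +0.02 points.
- 5% recrudescence (the planning value in 9.1) and 6% reinfection (the CQ arm of the trial in pregnant women in Ghana, 1.4.2.2): 95.10% against 95.00%, +0.10.
- 14% and 6%, both from that CQ arm: 86.27% against 86.00%, +0.27.
- 5% and 30%, as a high reinfection case: 95.53% against 95.00%, +0.53.
- 14% and 30%, well away from the planning value: 87.46% against 86.00%, +1.46.

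**Where the result turns.**
- No masking: the rule as written equals the truth in every case, a difference of 0.
- Half of later recrudescences found: the excess roughly halves.
- Recrudescence hazard doubled after reinfection (5% and 30%, all untreated), true response 94.47%: with no masking the written rule gives 94.47% and censoring every reinfection gives 95.00%, which is 0.53 too high. With half masking both are 0.53 too high. With full masking the written rule is 1.06 too high and censoring 0.53.

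**The case against.** A reader might infer that the PCR-corrected response is biased upward as the plan stands. The documents do not support that. By the protocol's own definitions reinfection is not failure, so counting such a woman as a responder is what the PCR correction intends. Footnote f foresees blots at every visit through Day 42, evaluated when the smear is positive, and does not stop at the first recurrence. Section 7.1 can be read as covering only the visit at which smears turn positive, but it need not be. No passage says that a new clone would hide the old one. This objection stands, and it removes any claim of bias from the rule alone.

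Also sound is that the upper figures rest on 5% to 10% reinfection per week, or 14% to 27% by Day 28, against 6% in the CQ arm from Ghana (with a further 10% there that PCR could not classify). Every woman also receives a bednet. With rates near those quoted in the protocol, the Day 28 excess is mostly 0.1 points or less, against a half-width of 3.5 points in a study that tests no hypothesis.

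Nor does 6.1.4 bar treatment of asymptomatic parasitaemia, so the untreated share is unknown. The antimalarial bullet can be read as the specific rule that overrides the completer bullet. The PCR-uncorrected analysis in 9.2.2 has no reinfection exemption and gives a more conservative figure beside the corrected one.

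Finally, censoring at reinfection is not free of bias: if reinfected women recrudesce more often, it can itself overstate response, as the doubled-hazard case shows.

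What survives is that one event is handled in two ways according to later treatment. The sensitivity analysis in 9.2.1 recodes premature discontinuation as failure and would not show the effect of this choice.

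**Conclusion.** The inconsistency is in the text: a PCR-confirmed reinfection ends follow-up in a woman given an antimalarial and leaves an untreated one at risk and responding up to Day 42. Whether this moves the estimate depends on masking, which the protocol does not settle. With full masking, recrudescence independent of reinfection and a true Day 28 response of about 94% or higher, the overstatement is a few hundredths of a point to about 0.6 points at Day 28 and up to about 1.7 points at Day 42. It grows with lower efficacy or a raised hazard after reinfection, and it is nil if later recrudescence remains fully detectable. All reinfection, untreated and masking rates are assumptions. The point is of low severity: a cheap improvement in consistency, not a demonstrated upward bias in the primary endpoint.

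**What to change.** In 9.2.1, and through it in the PCR-corrected analyses of 9.2.2, replace the reinfection part of the bullet with wording such as: subjects with PCR-confirmed reinfection are censored on the date of the smear that first shows it, whether or not an antimalarial is given; subjects given an antimalarial without parasitaemia are censored as now; where more than one rule applies, the earliest date is used.

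Report the present treatment-triggered rule as a sensitivity analysis. Neither rule is right under all assumptions, and showing both makes any difference visible.

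The cost is a sentence or two of analysis wording and one extra run, with no new data and no change to patient care. Slightly fewer women remain at risk at Days 28 to 42, so the intervals widen a little.

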Study drug is a fixed dose tablet of AZCQ containing 250 mg AZ and 155 mg CQ base. All subjects will be administered a single 3-day course of AZCQ IPTp regimen: a single dose of 1000 mg AZ/620 mg CQ base (4 fixed dose combination tablets of AZCQ: 250mg/155mg) administered *per os* (PO, orally) once daily for 3 days (Days 0, 1, 2). The first dose (on Day 0) and the third dose (on Day 2) will be administered under supervision by investigators at the antenatal care (ANC) facility, and the second dose on Day 1 will be administered under supervision by a field worker at home.

Main Endpoints

Primary Efficacy Endpoint

- Parasitological response (PCR corrected) at Day 28 post first dose of study medication.

Secondary Parasitological Clearance Endpoints

- Parasitological responses (PCR corrected) at Days 7, 14, 21, 35, and 42 post first dose of study medication;
- Parasitological responses (PCR uncorrected) at Days 7, 14, 21, 28, 35, and 42 post first dose of study medication;

- Parasite counts at each visit – number of asexual *P. falciparum* parasites per microliter of blood.

Pharmacokinetic Evaluation

- Pharmacokinetic exposure of AZCQ.

Safety Endpoints

- Safety and tolerability endpoints include spontaneously reported adverse events, temperature, hemoglobin concentrations, and the EIU safety assessment.

Statistical Methods

This study is designed to estimate the incidence for the primary endpoint. No statistical hypothesis will be tested.

The proportion of subjects with parasitological response (PCR corrected) at Day 28 following the first dose of study medication will be estimated for the primary endpoint using the modified intent-to-treat (MITT) and per protocol (PP) subject populations. Similar analysis will also be performed for an intent-to-treat (ITT) population will also be defined. The proportion will be estimated from the Kaplan-Meier curve of the time to the first occurrence of parasitological failure (PCR corrected). Use of the Kaplan-Meier curve/product limit estimator is recommended by WHO⁸ and has been used in analyzing primary efficacy endpoints in late stage antimalarial treatment clinical trials. See Section 9 for details.

An early analysis of the data will be performed on parasitological clearance endpoints including the primary endpoint, when all subjects complete Day 42 visit (ie, 42 days of follow-up post first dose), or withdraw from the study early.

[figure not shown]
Number of Subjects

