1.5.2.2. Clinical Efficacy of Azithromycin and Chloroquine Combination against *P. falciparum*

The clinical efficacy of AZ and CQ co-administration was investigated in several Phase 2/3 clinical studies. The efficacy outcomes from these studies are summarized below.

- A two-stage Phase 2 treatment trial in India demonstrated in vivo synergy between AZ and CQ against *P. falciparum* infection.⁵³ In the first stage of the trial (066-191), neither CQ monotherapy (27% efficacy at Day 28) nor AZ monotherapy (33% efficacy at Day 28) demonstrated adequate efficacy. During the second stage (066-191B), the combination of AZ and CQ demonstrated a 97% efficacy at Day 28. The dosing regimen used in this study was 1000 mg AZ once daily and 600 mg CQ base administered once daily for 3 days.
- Subsequently, the combination of AZ and CQ was evaluated for acute uncomplicated *falciparum* malaria in three Phase 2/3 studies, A0661120, A0661126 and A0661154 in India and South America regions. A dose response for AZ (on mg/kg basis) was observed. While efficacy rates observed in India (A0661120) and South America (A0661126) were suboptimal (86.3% and 57.1% respectively) with 1000 mg of AZ dose administered once daily for 3 days, the efficacy rate with the regimen containing higher AZ dose of 2000 mg in a subsequent study in A0661154 was 97.2% at Day 28 (96.4% at Colombia and 98.1% at India).⁸⁷
- Two further phase 2b/3 randomized comparative studies (A0661134 and A0661155) were conducted in sub-Saharan Africa in adults with the combination regimens of 1000 mg AZ and 600 mg CQ, once daily for 3-day treatment. Study 1134 was conducted in five countries in Africa including Ghana, Mali, Zambia, Kenya and Uganda. Study 1155 was conducted in Ghana, Mali, Zambia, Burkina Faso and Senegal. Both studies demonstrated efficacy, safety, and tolerability in the treatment of acute uncomplicated *falciparum* malaria. The efficacy rate was 98% (Appendix 1) and 100% on Day 28 for study A0661155 respectively. Both studies demonstrated efficacy, safety, and tolerability in the treatment of acute uncomplicated *falciparum* malaria. The Day 28 efficacy rates were 98%⁸⁸ and 100%⁸⁹ (PCR corrected), and 95% and 99% (PCR uncorrected) for study A0661134 and A0661155, respectively.

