9.1. Sample Size Determination

There will be approximately 166 subjects in the study. This will be a single arm, non-comparative estimation study and will not be powered for formal hypothesis testing. The sample size will yield a half width of a 2-sided 95% confidence interval to be ≤ 5 percentage points with probability=0.80 for the primary efficacy endpoint, using a large sample normal approximation to the binomial provided the true underlying incidence is $\geq 95\%$, and assuming approximately 10% will drop out.

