The proportion of subjects with parasitological response (PCR corrected) at Day 28 (primary) will be estimated from the Kaplan-Meier curve and its standard error estimated by the Greenwood formula. If less than 100%, a two-sided 95% confidence interval for the estimated proportion of subjects with parasitological response will be computed.

Additional sensitivity analyses will also be performed using the MITT and PP subject populations. The sensitivity analyses will consider premature discontinuation due to any reason as parasitological failure, if not already a parasitological failure due to a defined event. The same statistical methods will again be used to estimate the proportion of subjects with parasitological response (PCR corrected) at Day 28.

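### No confidence interval is planned if the estimated Day 28 response is 100%, although that interval is the study's only inference on response

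*Protocol*

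**What the plan says.** Section 9.2.1 says that the Day 28 PCR-corrected response "will be estimated from the Kaplan-Meier curve and its standard error estimated by the Greenwood formula". The next sentence reads: "If less than 100%, a two-sided 95% confidence interval for the estimated proportion of subjects with parasitological response will be computed". Nothing is given for an estimate of exactly 100%, and no scale (plain, log or log-log) is named for the interval.

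Section 9.2.2 analyses the secondary response endpoints in the same way, PCR corrected and uncorrected, so the rule applies at every visit.

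The synopsis states under Statistical Methods: "No statistical hypothesis will be tested". Section 9.1 sizes the study on precision alone: "a half width of a 2-sided 95% confidence interval to be ≤ 5 percentage points with probability=0.80 for the primary efficacy endpoint". That calculation treats the binomial count as normal, takes a true rate of 95% or more, and allows for about one woman in ten dropping out.

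On earlier results with the combination, section 1.5.2.2 states "The Day 28 efficacy rates were 98"% for A0661134 and 100% for A0661155, PCR corrected. Section 1.6.1 uses these two trials to justify the regimen.

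**The concern.** A single-arm study with no test and no decision threshold delivers an estimate and its uncertainty. The rule removes the uncertainty for one possible result, the most favourable one. That result is foreseeable, since one of the two trials behind the regimen produced it.

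A bare 100% from about 149 women would go into a supportive regulatory package without saying that the data are also compatible with a rate near 97.6%. The secondary visits share the gap. Early visits are the most exposed, because a Kaplan-Meier response curve can only fall with time.

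The study is open label, so a method chosen after a 100% result has been seen would be post hoc. Section 9 lets the analysis plan modify the protocol's methods, but major changes to the primary analysis must also appear in a protocol amendment.

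**Working it through.** **Inputs.** From section 9.1: 166 women, 10% dropout, planning rate 95%, half width 5 points, probability 0.80. From section 1.5.2.2: earlier rates of 98% and 100%.

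**The plan's own figure.** n = p(1−p)(z₀.₉₇₅ + z₀.₈₀)²/d² with p = 0.95 and d = 0.05 gives 149.13. Then 149.13/0.9 = 165.7, so 166. The sample size reproduces, and 149 is the planned evaluable number. This is a power-type formula; read literally, the half-width condition is met at n = 149 with probability 0.999. That is conservative and does not affect this point.

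**Chance of no interval.** The Kaplan-Meier estimate is 100% when no failure occurs by Day 28. For n evaluable women and true rate p this has probability pⁿ:

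- p = 0.95: 0.95¹⁴⁹ = 0.05%
- p = 0.98: 0.98¹⁴⁹ = 4.9%
- p = 0.985: 0.985¹⁴⁹ = 10.5%
- p = 0.99: 0.99¹⁴⁹ = 22.4%
- p = 0.995: 0.995¹⁴⁹ = 47.4%

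A Kaplan-Meier simulation (166 women, 10% dropout by Day 28, failures spread evenly over Days 7 to 28, 40,000 runs) gives 4.4%, 21.0% and 45.4% at 98%, 99% and 99.5%. With no dropout (n = 166) the figures are 3.5%, 18.9% and 43.5%. None of this depends on the scale: plain and log-log Greenwood intervals both break down with no failures.

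**What could be reported instead.** With no failures in n, the exact (Clopper-Pearson) two-sided 95% lower limit is 0.025^(1/n). For n = 149 this is 97.6%; for n = 140 it is 97.4% and for n = 166 it is 97.8%. The Wilson lower limit at 149/149 is 97.5%.

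**Conditional part: if the interval is plain, S ± 1.96·SE.** Without censoring, Greenwood equals the binomial standard error. At n = 149:

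| Failures | Plain | Clopper-Pearson | Wilson | Log-log |
|---|---|---|---|---|
| 1 | 98.0% to 100.6% | 96.3% to 99.98% | 96.3% to 99.9% | 95.3% to 99.9% |
| 2 | 96.8% to 100.5% | 95.2% to 99.8% | 95.2% to 99.6% | 94.7% to 99.7% |
| 3 | 95.7% to 100.2% | 94.2% to 99.6% | 94.2% to 99.3% | 93.9% to 99.3% |
| 4 | 94.7% to 99.9% | 93.3% to 99.3% | 93.3% to 99.0% | 93.0% to 99.0% |

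The plain upper limit passes 100% with 1 to 3 failures. That has probability 60% at a true 98%, 71% at 99% and 52% at 99.5%.

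Exact coverage of the plain interval, given that one is computed:

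| True rate | 95% | 97% | 98% | 98.5% | 99% |
|---|---|---|---|---|---|
| Coverage | 93.6% | 94.5% | 83.9% | 99.8% | 99.9% |

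The simulation gives 86.6% at 98%. The dip has one main cause: at 148/149 the lower limit is 98.02%, just above the true rate, and that outcome has probability 149 × 0.02 × 0.98¹⁴⁸ = 15%.

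**Alternatives, exact at n = 149.** Coverage at 98%, 99% and 99.5% is 96.9%, 93.7% and 96.1% for Wilson, and 98.9%, 98.3% and 99.3% for Clopper-Pearson. Log-log, when computed, covers 0.9197/(1 − 0.0493) = 96.7% at 98% and 0.7129/(1 − 0.2237) = 91.8% at 99%.

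**The case against.** The strongest reply is that the protocol fixes only the Greenwood standard error. A log-log interval uses the same standard error, stays within 0% to 100%, and also needs a clause for an estimate of 100%. The scale is commonly left to the analysis plan, which is not at hand. This stands: limits above 100% and low coverage cannot be charged to the protocol as fact. The normal approximation in section 9.1 suggests a plain interval, but it concerns sample size.

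A reader might also infer that the planned interval fails throughout 98% to 100%. The figures do not support that, even on the plain reading. Undercoverage when an interval is computed is local to about 98%; from about 98.5% upward the interval covers. Overall coverage of 77.6% at 99% arises from counting the 22.4% of trials without an interval as misses, so it is not a second defect.

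The 98% and 100% came from symptomatic, non-pregnant adults. This trial enrols asymptomatic women in a first or second pregnancy and plans on 95% or more. At 95% the missing interval is negligible. This also stands: the high range is plausible, not assured.

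Finally, the study is supportive, a reader could work out an exact limit from the number at risk, and the sensitivity analysis counts discontinuations as failures. With 10% dropout that analysis falls near 90% and has an interval. This lowers the stakes, but it estimates a different quantity and cannot supply the primary limit.

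**Conclusion.** The point holds in a limited form. The protocol states a rule that leaves the primary estimate, and the same estimate at other visits, without an interval at 100%, and offers nothing in its place. The chance of this is about 5% to 47% for true rates of 98% to 99.5%, and about 0.05% at 95%. This rests on about 149 evaluable women and holds on either scale.

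Limits above 100%, and coverage of about 84% to 87% near a true 98%, follow only if the interval is untransformed.

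This should be fixed. It does not invalidate the design: the estimator is sound, no decision threshold depends on the limit, and the gap arises for one outcome.

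**What to change.** In section 9.2.1, remove the condition that the estimate be below 100%, and pre-specify an interval that is valid at the boundary:

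- **No failures by the visit:** give an exact (Clopper-Pearson) lower limit based on the number still at risk at that visit, with an upper limit of 100%. For 149/149 this is 97.6% to 100%.
- **Estimate below 100%:** name a bounded interval. One choice is Wilson on the effective sample size n_eff = S(1−S)/SE², with the Greenwood SE. Log-log Greenwood is another, though its coverage dips to about 92% at a true 99%.
- **Scope:** apply the rule to all visits, PCR corrected and uncorrected, and to each analysis population.

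The cost is a sentence in the protocol and a few lines of code, with no extra data or women. The reported lower limit becomes slightly less favourable: compared with a plain interval, Wilson is about 1.7 points lower at 148/149 (96.3% against 98.0%) and 1.5 points lower at 146/149 (94.2% against 95.7%).
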